Early Assisted Discharge for COPD Exacerbations With Telemonitoring.

ClinicalTrials.gov, NCT01951261.

Versión 1. 01/02/2012

**Department Pneumology Hospital Puerta de Hierro and Carlos III Health
Institute.**

**Reseachers: [name], [name], [name], [name].**

Protocol:

The TELEMED-COPD study is a randomized clinical trial with 2 parallel groups (both with early discharge; intervention group: home hospitalization with telemonitoring / control group: traditional follow-up based on face-to-face visits by healthcare personnel). It was carried out at the Puerta de Hierro Hospital from March 2012 to July 2018. Once the informed consent was given by the participants, they were randomly distributed between the two groups using a table of pseudo-randomized numbers in variable blocks generated by computer. The randomization sequence was kept hidden by the randomization system itself. Substitution of patients withdrawn from the study was not performed.

Participation criteria:

Patient admitted with exacerbation of COPD in the Pulmonology Service, with no age limit and who, after an initial phase of clinical stabilization not exceeding 4 days, meets the inclusion criteria: 1) Diagnosis of COPD (prior or during admission according to GOLD 2020), 2) absence of serious decompensated concomitant diseases, 3) arterial blood gas: pH > 7.35, pO₂ > 50 mmHg with O₂ at maximum 3 bpm, Oxygen saturation > 90%, pCO₂ < 55, 4) afebrile more than 48 h, 5) need for administration of maximum bronchodilators every 6 hours, 6) corticosteroids < 40mg / 12 hours, 7) chest radiograph without new onset pathology, 8) subjective improvement, and 9) adequate family environment.

Exclusion criteria: 1) Neoplasms or other end-stage chronic diseases, 2) alcoholism, 3) need for intravenous medication, 4) inability to understand the program and participate in it, 5) have required ICU care or need mechanical ventilation non-invasive during exacerbation, 6) institutionalized patient.

Withdrawal criteria: unsuccessful inability to use telemonitoring, complications derived from hospital admission or at the express request of the patient.

Study variables:

The main variable was the time to the first exacerbation after discharge (exacerbation was defined as an acute and sustained deterioration in the patient's clinical condition, greater than the daily fluctuation and requiring a change in the usual medication)

The secondary variables analyzed were: the use of healthcare resources measured as the number of home visits by healthcare personnel (scheduled and unscheduled), average time hospitalized at home, exacerbations after discharge and readmissions for this reason. Other secondary variables: 1) degree of satisfaction with home care (Satisfad questionnaire¹⁰) and for the intervention group also a specific survey, consisting of four questions with answers using a five-level Likert scale (assessment from 1 to 5, from lower to greater satisfaction and / or need for help) and a fifth open-ended question about their experience with the monitor. 2) Measurement of anxiety and depression using the STAI questionnaire (trait-trend) in the home hospitalization phase. 3) Impact on well-being and quality of life using the CAT (COPD Assessment Test) questionnaire. 4) Therapeutic compliance through the Morinsky-Green-Levine questionnaire at the beginning and at the sixth month; additionally for the intervention group, adherence to telemonitoring was determined based on compliance with the protocolized shipments.

Comparative interventions:

The first phase of the study was hospitalization at home (with or without telemonitoring depending on the assigned group) and the second phase was follow-up after medical discharge (identical for both groups, without telemonitoring); with one consultation a month and another at 6 months. In these consultations, outpatient and / or hospital exacerbations were collected, as well as other study variables.

Control group (conventional home hospitalization):

** Visiting regime: a first visit is made in the hospital (doctor and nurse who will follow up), making a clinical evaluation and management of the bronchodilators.

The rest of the visits are daily at home and will initially be carried out only by the infirmary, except for the final visit in which the doctor accompanies him to discharge the patient, if he meets the following criteria:

- Clinical stability, with recovery from daily activities, with dyspnea similar to its baseline.
- Saturation levels > 90% with or without oxygen and lower requirements for short acting adrenergic beta2 agonists.
- Correct use of medication.

Constants are taken, physical examination, clinical evaluation and health education (involving knowledge of your disease, inhalation technique, therapeutic compliance, exercise respiratory, nutritional advice and smoking cessation if needed).

Intervention group (Home Hospitalization with Telemedicine):

** Regimen of home visits: 1) An initial visit to the hospital (doctor and nurse), 2) an intermediate visit by the nurse, 3) the last visit :discharged the patient by the nurse and the doctor. The nursing actions in the visits, the hours of attention and the discharge criteria are the same as those detailed in the control group. On the first day that the patient was at home, he received a visit from the technician, who installed the telemonitoring equipment and trained the patient and family members in its handling (leaving them a contact telephone number for incidents).

** Telemonitoring: to carry it out, a multi-parameter recording equipment with communication capacity over the GSM network was used, which sent the data to an online web platform, which was reviewed by the responsible doctor.

The parameters recorded were: ECG (leads I, II, III), O2 Saturation (%), heart rate, blood pressure, temperature and respiratory rate.

The patient sent them twice a day (morning and afternoon), at approximately the same time (weekdays), and later received a phone call from the doctor to assess their clinical situation (symptoms, degree of dyspnea (mMRC), changes in appearance and amount of sputum, compliance and complications) and decide the action to follow.

Thresholds of normal intervals were established in the before mentioned parameters, outside these ranges, a warning was generated in the form of sms

to the medical phone. If an intervention was necessary, they contacted the patient and explained the action plan (home visit, going to the emergency room, changing medication, etc.).

Statistic analysis:

The main hypothesis is to verify that after the early discharge, the health results caused by the experimental treatment (intervention) are not inferior to the reference treatment (control). The scientific literature states that the median of the “exacerbation-free time” of the reference treatment is 2 months, and therefore, the “non-inferiority” condition requires that the median in the experimental group be similar. It is considered appropriate to set a “noninferiority” limit of 0.60 units in multiplicative terms with respect to the reference treatment; In other words, an attempt will be made to demonstrate that the experimental treatment provides at least a median of the exacerbation-free time of not less than 1.2 months (36 days), if it is exacerbated before this period of time the study didn't comply the “non inferiority” condition. Thus, we calculated that a minimum sample of 58 patients per treatment group (in total 116) was required to ensure a power of 80% and a significance level of 5%. Exacerbation-free time was defined as the interval between discharge from the home and the moment of exacerbation, until the end of the study when it did not occur or in the event of loss of follow-up until the last recorded time. All analyzes were performed according to the principle of intention to treat.

The statistical analysis of the main variable was carried out using the Kaplan-Meier method and the statistical test of the log-rank test.

The comparison between the two groups was made with the Student t test for continuous variables and the non-parametric Mann-Whitney test when the normality test was rejected.

The statistical package used was Stata V.15.1.

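### Failure to use telemonitoring is a reason for withdrawal from the study that only the intervention arm can meet, and the plan does not say that these patients are still followed

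*Combined protocol and SAP*

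**What the plan says.** The paragraph on withdrawal, under Participation criteria, reads: "Withdrawal criteria: unsuccessful inability to use telemonitoring, complications derived from hospital admission or at the express request of the patient". The wording of the first reason is garbled; I read it as failure to manage the equipment. The opening Protocol section adds: "Substitution of patients withdrawn from the study was not performed". On that wording, the exit is from the study and not only from the device.

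The Intervention group section places the equipment after randomisation: "On the first day that the patient was at home, he received a visit from the technician, who installed the telemonitoring equipment". Under Comparative interventions, "the second phase was follow-up after medical discharge (identical for both groups, without telemonitoring". Exacerbations are collected at the visits of that second phase, "with one consultation a month and another at 6 months".

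Statistic analysis sets the time origin: "Exacerbation-free time was defined as the interval between discharge from the home and the moment of exacerbation". Patients without an event are censored at the end of the study or, "in the event of loss of follow-up until the last recorded time". The same section declares intention to treat for all analyses.

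**The concern.** Intention to treat needs two things for every randomised patient: outcome data and a place in the analysis. The plan gives neither for a patient withdrawn in the home phase. The loss of follow-up rule can cover someone who leaves after home discharge. It does not clearly cover someone who leaves earlier, because their last recorded time may precede the clock's start.

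Control patients have no device to fail with, so a control patient of the same kind stays in. If those lost carry a different exacerbation risk, the remaining arms are no longer comparable. The trial claims non-inferiority, so losing higher-risk patients from the telemonitoring arm would make a false claim easier to reach.

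The other two reasons are less clear-cut. A patient's own request can arise in either arm. If the complications criterion refers to the index hospital stay, before care differs by arm, imbalance is less likely.

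**Working it through.** **Who can meet the criterion, and when.** The device goes in on the first day at home, in one arm, and is absent after medical discharge. Failure to use it therefore falls after randomisation and before home discharge, in the intervention arm only. The primary clock starts at that discharge and the outcome visits follow it. No section links a withdrawn patient to those visits or states a discharge date for them.

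**Inputs.** From Statistic analysis: control median 2 months, margin 0.60 on the ratio of medians, 58 per arm, 80% power, 5% significance. From Comparative interventions: last visit at 6 months. Assumed: exponential times (so the margin is a hazard ratio of 1/0.60 = 1.67), a one-sided test, and a Cox confidence bound. The plan does not state sidedness and names Kaplan-Meier and log-rank.

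**The plan's own sample size.** Freedman's formula gives (1.60/0.40)² × (1.645 + 0.842)² = 16 × 6.18, or 99 events. The chance of an event by 6 months is 1 − 0.5³ = 0.875. Then 99/0.875 = 113.1, or 57 per arm against the stated 58. With 116 × 0.875 = 101.5 events, Schoenfeld power is Φ(½√101.5 × ln 1.667 − 1.645) = Φ(0.93) = 82%. A two-sided 5% test gives 73%, so one-sided 5% fits the stated 80% better at 6 months. It is not certain: two-sided power would be 78.6% if all 116 patients had an event.

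**Loss of numbers alone.** Dropping 6 intervention patients leaves (52 + 58) × 0.875 = 96 events and 80.4% power. Dropping 12 leaves 91 events and 78.1%. This part is small.

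**Selective loss.** The simulation used 12,000 trials per cell. The same share of patients in both arms has k times the hazard of the rest, and only those in the telemonitoring arm are excluded. Non-inferiority is declared if log HR + 1.645 SE < log(1/0.60). The treatment effect is set so that the hazard ratio with everyone kept is 1.67 for the error rate, and 1 for power.

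| Share of telemonitoring arm excluded | 5% (about 3 of 58) | 10% (about 6) | 20% (about 12) |
|---|---|---|---|
| False non-inferiority, k = 2 | 6.4% | 7.9% | 12.3% |
| False non-inferiority, k = 1 | 5.3% | 5.1% | 4.6% |
| Power, k = 1 | 81% | 80% | 78% |
| False non-inferiority, k = 0.5 | 2.9% | 1.7% | 0.5% |
| Power, k = 0.5 | 76% | 69% | 53% |

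At 10% excluded, the average hazard ratio moves from 1.67 to 1.59 (k = 2) or 1.83 (k = 0.5), and stays at 1.67 for k = 1. With everyone kept, the error is 4.6–5.4% and power 81–82%. The Monte Carlo error is about 0.2 points at 5%. A repeat with 6,000 trials per cell gave 6.6%, 8.1% and 12.4% for k = 2. With a one-sided 2.5% test, 10% excluded at k = 2 gives 4.5% against 2.5%.

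**Hand check.** Hold the whole telemonitoring arm's median at 1.2 months, with 10% of the arm at twice the hazard h of the rest, and treat the control arm as homogeneous. Solving 0.9e^(−1.2h) + 0.1e^(−2.4h) = 0.5 gives a median of 1.291 months for the rest, a ratio of 1.291/2 = 0.645. The error is then about 10%. Shares of 5% and 20% give about 7% and 18%. These exceed the simulated values because this check fixes the median ratio rather than the average hazard ratio and uses a different control arm. The table is the more conservative illustration.

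**The case against.** The strongest reply is that the plan excludes nobody. It declares intention to treat and says only that withdrawn patients were not replaced. A reader might infer that the rule removes patients and so defeats intention to treat. The documents do not support that; they leave the handling unstated, and the supported word is *may*.

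A reader might also infer that anyone withdrawn in the home phase has no time origin. That too goes beyond the text. The discharge criteria are clinical and common to both arms, and none depends on the device, so such a patient could be discharged and have the date recorded. The plan does not say whether this happens.

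The size is open to challenge as well. Nothing in the documents ties difficulty with the device to a doubled hazard. Several provisions should keep failures few: the exclusion for "inability to understand the program and participate in it", the required family environment, and the technician who trains patient and relatives and leaves a number for incidents. These make the 20% column hard to credit. They do not empty the category, since the protocol still keeps a withdrawal criterion for it.

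The loss of follow-up rule can reasonably be read to cover withdrawal after home discharge, where the arm-specific criterion cannot operate. The point is therefore confined to the home phase.

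**Conclusion.** The point holds in this limited form. A stated rule sends patients out of the study for a reason that only one arm can meet, before the primary clock starts, and no text keeps them under follow-up. The intention-to-treat sentence states the aim without supplying the means.

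It would be tempting to conclude that the result is biased towards non-inferiority. The documents show neither a withdrawal rate nor the risk of those withdrawn, so the direction is unknown. False non-inferiority of about 6%, 8% or 12% requires that 5%, 10% or 20% of the telemonitoring arm be lost at twice the hazard of the rest. Equal hazard leaves it at about 5%. Half the hazard makes the test conservative and costs power. All of these rest on the assumed shares, exponential times, 6 months of follow-up and a one-sided 5% Cox bound. A reader cannot tell which case applied without withdrawals shown by arm and reason.

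**What to change.** Make failure to use telemonitoring, and complications, reasons to stop telemonitoring or the home programme, not the study.

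- Patients who cannot use the device continue with conventional home visits until they meet the shared discharge criteria. Their exacerbation-free time starts at that discharge, as for everyone else. Starting it on the day they leave telemonitoring would begin the clock at a less recovered state than in controls.
- Follow all these patients at the existing consultations and analyse them in their assigned arm.
- Include patients who never reach home discharge, for example those readmitted from the home phase, through an analysis from randomisation that counts a deterioration in the home phase as an event.
- Censor patients who refuse further follow-up at their last recorded time.
- Report withdrawals by arm, reason and timing relative to home discharge.

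The protocol describes the trial as carried out to July 2018. For patients already withdrawn, what remains is to retrieve discharge and exacerbation dates from records where possible and to publish the withdrawal table.

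The cost is a reworded rule, one table, a few extra nurse visits and some record retrieval. The estimate may become less favourable to telemonitoring.

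### Compliance is measured at the start and at month 6, but neither between-group test the plan names adjusts for the starting score

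*Combined protocol and SAP*

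**What the plan says.** The Study variables section lists compliance among the secondary variables, assessed by "questionnaire at the beginning and at the sixth month". It is the only secondary variable given both a starting and a six-month assessment.

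The Statistic analysis section assigns Kaplan-Meier and log-rank methods to the main variable. For everything else there is one general sentence: "The comparison between the two groups was made with the Student t test for continuous variables and the non-parametric Mann-Whitney test", the second test applying when normality is rejected. No covariate, regression or mixed model is named for any variable, and no test is given for categorical variables.

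Four things about compliance are left open:

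- whether the month-6 score or the change from the start is compared;
- whether the score is treated as numeric, ordinal or yes/no;
- whether the starting questionnaire comes before randomisation;
- how missing month-6 questionnaires are handled.

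**The concern.** A score taken before randomisation usually predicts the same score six months later. An unadjusted month-6 comparison ignores that and carries any chance difference in starting compliance into the result. A change score does not fully cure this: unless the month-6 score moves one-for-one with the starting score, subtraction over-corrects.

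With 58 patients per arm, a chance difference at the start is plausible. Compliance also bears on the comparison. Health education in both arms covers it, and in the telemonitoring arm the doctor also asks about it by telephone. At stake are the width of the interval for this outcome and the freedom to choose month-6, change or dichotomised scores after the data are seen.

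**Working it through.** **1. The plan's own figure.** Nothing is calculated for compliance. The only sample size is for the main variable: "a minimum sample of 58 patients per treatment group (in total 116) was required", at 80% power and 5% significance. Its inputs are that "the median of the “exacerbation-free time” of the reference treatment is 2 months" and "a “noninferiority” limit of 0.60 units in multiplicative terms with respect to the reference treatment".

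- Freedman events, one-sided 5%: (1.645 + 0.842)² × ((1 + 0.6)/(1 − 0.6))² = 6.18 × 16 = 98.9, so 99.
- Exponential event probability over 6 months with a 2-month median: 1 − 0.5³ = 0.875.
- Patients: 99/0.875 = 113.1, or 57 per arm, against the stated 58.

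The match needs a one-sided 5% level and a six-month event probability, neither of which the plan states for this calculation. Two-sided, the same route gives 126 events and 126/0.875 = 144 patients, or 72 per arm. Compliance enters nowhere, so 58 per arm serves below only as the number of patients available.

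**2. Against a t test on the month-6 score.** For a numeric score, linear ANCOVA multiplies the variance of the group difference by 1 − r². The equivalent size per arm is 58/(1 − r²). At two-sided 5% and 80% power the unadjusted detectable difference is (1.960 + 0.842) × √(2/58) = 0.52 SD, which adjustment multiplies by √(1 − r²). Every r is an assumption.

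| Assumed r | 1 − r² | Variance cut | Equivalent per arm | Detectable difference (SD) |
|---|---|---|---|---|
| 0 | 1.00 | 0% | 58 | 0.52 |
| 0.2 | 0.96 | 4% | 60 | 0.51 |
| 0.3 | 0.91 | 9% | 64 | 0.50 |
| 0.5 | 0.75 | 25% | 77 | 0.45 |
| 0.6 | 0.64 | 36% | 91 | 0.42 |

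This takes both scores as complete in all 58 per arm.

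**3. Against a t test on change.** With equal variances at the two times, the change score has relative variance 2(1 − r). The ANCOVA ratio is (1 − r²)/(2(1 − r)) = (1 + r)/2. That is 0.65 at r = 0.3, 0.75 at 0.5 and 0.80 at 0.6, or cuts of 35%, 25% and 20%.

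**4. Coarse scoring.** Grouping a score lowers the observed correlation. A simulation with 58 per arm, comparing linear adjustment with an unadjusted month-6 difference, gave:

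| Underlying r | Score | Observed r | Simulated variance factor | 1 − (observed r)² |
|---|---|---|---|---|
| 0.3 | 5-level | 0.262 | 0.923 | 0.931 |
| 0.3 | yes/no | 0.195 | 0.967 | 0.962 |
| 0.5 | 5-level | 0.449 | 0.804 | 0.798 |
| 0.5 | yes/no | 0.331 | 0.897 | 0.890 |

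The cut is therefore about 8% or 20% for a 5-level score and about 3% or 10% for a yes/no score (risk-difference scale). At r = 0 the simulated factor was 1.005 to 1.012 across score types, so an uninformative covariate costs about 1%.

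**The case against.** The strongest reply is that the plan never states the compliance analysis. A reader might infer that the starting score goes unused, but the documents do not support that. The general sentence names no outcome and no time point, and a t test on change would use the starting score. What stands is narrower: no adjustment for it is named, and for a numeric score ANCOVA is, in large samples, at least as precise as either t test.

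Three further replies have force.

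- **Score type.** The named tests are for continuous variables, and compliance may be scored in categories. The 1 − r² figures do not carry over to an odds ratio. Logistic adjustment changes the quantity estimated and does not shrink the standard error of the log odds ratio.
- **Timing.** Randomisation follows consent, and each arm's regimen opens with a hospital visit. The plan does not place the starting questionnaire relative to either, so calling the gain free assumes a complete, pre-randomisation score.
- **Validity.** Randomisation already makes the unadjusted comparison unbiased, and its test allows for chance imbalance. The argument is about precision, not about correcting a bias.

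A reader might also extend the point to the CAT questionnaire. The plan gives no assessment times for CAT, so there is no basis for that.

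**Conclusion.** The point holds as an optional improvement to one secondary outcome. The plan schedules compliance at two times and names only unadjusted tests.

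The size cannot be read from the documents, which give no correlation, standard deviation or score type. For a numeric score compared at month 6 only, it runs from nothing at r = 0 to 36% of the variance at r = 0.6. Against a change score with equal variances, the gain is largest when r is low. Coarse scoring shrinks the gain over a month-6-only comparison.

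All of this assumes a starting score that is complete and taken before randomisation. A reader might infer that the trial's conclusion is weakened. It is not: the log-rank comparison of the main variable, the non-inferiority margin and the sample size of 116 do not involve the compliance score.

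**What to change.** State how the compliance questionnaire is scored, and confirm that the starting score is taken before randomisation. If so, compare month-6 compliance between arms with the starting score as a covariate:

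- for a numeric score, linear ANCOVA, reporting the adjusted difference with a 95% interval;
- for an ordered or yes/no score, an ordinal or binary model reported as a standardised group difference (for example, a difference in proportions averaged over the starting scores) with a 95% interval.

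Say also how missing starting and month-6 scores are handled. If the starting score was taken after randomisation, do not adjust for it; state the unadjusted month-6 comparison as the analysis.

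The cost is a few sentences, since both assessments are already scheduled. However, the document describes the trial as already carried out, to July 2018. If the outcome data have been examined, present the adjusted result as post hoc, beside the unadjusted one.

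### Resource use is measured mainly by home visits, which the protocol lowers by design in the telemonitoring arm, while that arm's doctor calls and platform review are not counted

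*Combined protocol and SAP*

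**What the plan says.** The secondary variables, listed under Study variables, include "the use of healthcare resources measured as the number of home visits by healthcare personnel (scheduled and unscheduled), average time hospitalized at home". The same sentence goes on to exacerbations after discharge and the readmissions they cause.

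Under Comparative interventions, both arms begin with a visit in hospital. For the control group, "The rest of the visits are daily at home and will initially be carried out only by the infirmary"; a doctor joins the nurse at the final visit. No phone calls are described for this arm.

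The intervention group's numbered regimen continues after the hospital visit with "2) an intermediate visit by the nurse, 3) the last visit :discharged the patient by the nurse and the doctor", that is, two home visits. Outside that numbering, on the first day at home, "he received a visit from the technician, who installed the telemonitoring equipment and trained the patient and family members in its handling". The monitor "sent the data to an online web platform, which was reviewed by the responsible doctor". On calls, the text says: "The patient sent them twice a day (morning and afternoon), at approximately the same time (weekdays), and later received a phone call from the doctor". Readings outside the set limits send a text-message warning to the medical phone, and the patient is contacted if action is needed.

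Shipments are tracked, but under compliance: "adherence to telemonitoring was determined based on compliance with the protocolized shipments".

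**The concern.** As a count of home visits, the variable is sound. The difficulty is that it stands as the main measure of resource use for two care packages that use different kinds of contact. Telemonitoring removes nurse visits and adds doctor calls, doctor review of transmitted data, and a technician's visit. The removal is counted. The calls and review are not, and the technician's visit is counted only if a technician is classed as healthcare personnel, which the plan leaves open.

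The calls are not a courtesy. In them the doctor goes through symptoms, dyspnoea, sputum, compliance and complications and decides what to do next, which is part of the clinical work of the visits they replace.

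Because the visit schedules are set by protocol, the difference in scheduled visits mostly reflects the design. If it were reported as lower use of healthcare resources, the saving would be overstated and a shift from nurse time to doctor time would not be seen.

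**Working it through.** The plan gives no figure for this comparison, so there is nothing to reproduce. The check counts contacts per patient from the two schedules.

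**Inputs from the plan**
- Control: one home visit a day, with the doctor joining at the last.
- Intervention: 2 home visits, with the doctor joining at the last, plus 1 technician visit.
- Shipments: twice a day on weekdays, followed by a phone call (singular).

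**Assumptions, because the plan gives no figures**
- Home stay of 6 days, starting Monday to Friday in equal shares.
- Control home visits counted from day 1.
- One call per shipping day. Low count: no call on the installation and discharge days. High count: a call on every weekday of the stay.
- 10 to 20 minutes per call and 60 per home visit.
- No unscheduled or alert-triggered contacts.

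**Visits saved.** 6 − 2 = 4. The doctor attends one home visit in each arm, so all four are nurse visits.

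**Uncounted calls**

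| Start day | Weekdays in days 2–5 (low) | Weekdays in days 1–6 (high) |
|---|---|---|
| Monday | 4 | 5 |
| Tuesday | 3 | 4 |
| Wednesday | 2 | 4 |
| Thursday | 2 | 4 |
| Friday | 2 | 4 |
| Mean | 13/5 = 2.6 | 21/5 = 4.2 |

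Calls per visit saved: 2.6/4 = 0.65 to 4.2/4 = 1.05. These are averages over start days. For a Wednesday to Friday start, the low count gives 2/4 = 0.50. A 5-day stay starting on Thursday gives 1 call for 3 visits saved, or 0.33.

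**Time offset** = calls × minutes per call ÷ (visits saved × 60).
- Low: 2.6 × 10 ÷ 240 = 11%.
- High: 4.2 × 20 ÷ 240 = 35%.

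**Technician.** One visit is 1/4 = 25% of the difference in home visits. If it is also given 60 minutes, the offset becomes (26 + 60)/240 = 36% to (84 + 60)/240 = 60%.

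**Other readings, 6-day stay**
- Control also visited on weekdays only: 4.2 − 2 = 2.2 visits saved, or 132 minutes. Offset 26/132 = 20% to 84/132 = 64%.
- Control's first home visit on day 2: 5 − 2 = 3 visits saved, or 180 minutes. Offset 26/180 = 14% to 84/180 = 47%.
- Shipments seven days a week with a call after each: 12 calls. At 20 minutes, 12 × 20 ÷ 240 = 100%.

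**The case against.** The strongest reply is that the plan says openly what it counts and claims nothing more. The hypothesis under Statistic analysis is non-inferiority of health results, and nowhere is a cost, staff-time or resource-saving hypothesis stated. Any harm therefore depends on how a secondary result is later read. This stands, and it limits the weight of the point. It does not remove it, because the plan itself names the variable use of healthcare resources.

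Second, the list is not blind to costs on the intervention side. Unscheduled home visits count, and so do time in home hospitalization, exacerbations and readmissions; alert-driven visits and readmissions would tell against telemonitoring. A reader might infer that the resource measures are wholly one-sided, and the text does not support that. The gap is narrower: remote doctor contact, and possibly one technician visit.

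Third, a reader might infer that the saving disappears once calls are counted. The 100% offset needs shipments seven days a week, two calls a day and 20 minutes per call. The text says weekdays and refers to a call in the singular, and it gives no minutes at all. On the reading closest to the text, most of the visit time saved remains.

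Last, the number of shipments recorded for adherence might look like an upper limit on calls. It is not: alert-triggered calls can come on top. The plan also does not say that calls were logged or that shipments were stored by day.

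**Conclusion.** The point holds as a gap in a secondary variable. The main measure of resource use is set lower in the intervention arm by protocol, the doctor's calls and platform review described only for that arm appear in no listed variable, and the technician's visit has no stated status. The other listed outcomes do not capture remote doctor contact.

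On the closest reading, a 6-day stay saves four nurse visits at the price of about 2.6 to 4.2 doctor calls and one technician visit, and the calls offset roughly 11% to 35% of the visit time saved. These sizes rest on an assumed stay length and assumed minutes, so they illustrate the scale and are not estimates from the trial. They also leave out any review time beyond the call minutes. The omission itself depends on none of these assumptions.

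The documents do not show that telemonitoring fails to save resources, and they do not settle that the technician's visit is left out. The time-to-exacerbation analysis and the sample size are unaffected. This is an improvement to consider, not an error that threatens the trial's main conclusion.

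**What to change.** The protocol describes the trial as already carried out, so the changes concern definition and reporting.

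1. Label the present count as home visits, and state whether the technician's visit is included.
2. Report contacts per patient in the home phase by type and arm: nurse, doctor and technician home visits, and doctor phone calls, including alert-triggered calls and any calls to control patients where recorded.
3. If calls were not logged, estimate them from the days with a shipment, where the adherence record allows. Present the result as an estimate, not a bound.
4. State on which days visits, shipments and calls ran in each arm.
5. Do not conclude lower use of healthcare resources from home visits alone. If contacts by type cannot be assembled, limit the conclusion to face-to-face home visits.

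A staff-time table, with nurse and doctor time shown separately and the assumed minutes stated and varied, is optional sensitivity work.

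The cost is a sentence or two of definition, one on operating days, and a few table rows. The technician's visit is one per intervention patient by protocol and needs no new data. The downsides are that the apparent saving becomes smaller and that call counts may be approximate.
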